5. STUDY DESIGN

Subjects will receive up to 10 laser treatments on their unwanted tattoo. The study subjects will return to the investigator site for follow-up evaluations. See section 5.4 for schedule and visit details.

5.1 Subject Assignment

All potential subjects will undergo a pre-screening interview where their medical history will be reviewed and inclusion/exclusion criteria verified. Subjects meeting the criteria for enrollment in the study will sign the informed consent form and be assigned a subject identification number. Subject identification numbers will be generated chronologically and assigned only to subjects who have met all inclusion/exclusion criteria and signed the informed consent form. Subjects will be de-identified through their subject identification number, which will be stored in a secure location.

5.2 Screening

- Consent must be signed.
- Medical history of each subject will be reviewed and inclusion/exclusion criteria verified. A limited physical exam (no pelvic and no rectal exam).
- Subjects meeting the criteria for enrollment in the study will sign the informed consent form and be assigned a subject identification number.

5.3 Laser Treatment

5.3.1 Pre-Treatment

- Photographs will be taken of the treatment area(s).
- Female subjects will be asked if they are pregnant and the date of their last menstrual cycle (no pregnancy testing will be conducted).

5.3.2 Procedure

- All laser operators and subjects will wear protective eye glasses during the laser treatments
- Subjects will receive up to 10 treatments, administered every 4-12 weeks.
- Adjunctive tissue cooling with chilled air (Zimmer Cooler) will be used during and/or after treatment to enhance comfort. If subjects require additional means of reducing treatment or post-treatment discomfort, an optional application of topical anesthesia, such as EMLA® , ElaMax® or BLT cream for up to 60 minutes prior to treatment may be used at the discretion of the Investigator.

5.3.3 Technique

- The appropriate parameters including the number of pulses will be determined by the physician.
- The laser hand piece distance gauge tip will be in contact with the skin.

5.3.4 Post Treatment

- Standard post-op wound care instructions will be reviewed.
- Aquaphor will be applied to the treatment and it will be covered with a non stick pad. The subjects will be instructed to change the pad twice per day for one week.
- Subjects may resume normal activities after treatment.
- If treatment area is in a location that is exposed to the sun, the treatment area should remain covered at all times. If this is not possible, sun block with a broad spectrum UVA, UVB sunscreen of SPF 30 or higher should be applied to the treated area every 2 hours when exposed to sun and, and should apply protection throughout the study.
- This information is also included in the Informed Consent Form.

5.3.5 Unscheduled Visits

An unscheduled visit may be performed at any time during the study at the subject's request or as deemed necessary by the site Investigator. The date and reason for the unscheduled visit will be recorded in the source documentation.

5.4 Subject visit Schedule

- Visits will be required per schedule below:

Procedure	Screening /Baseline	Treatment 1-10 (every 4-12 weeks)	2 Month Follow Up (+/- 1 Month)
Consent	X		
Medical History	X		
Photos	X	X	X
Treatment		X	
Events Assessment	X	X	X
Satisfaction Questionnaire (Subject and PI)			X

The sponsor anticipates that all subjects can be enrolled within 2 months. Treatment and follow-up on the last subject entered into the study will add at least another 12 months to the study duration. Subject participation in the study is expected to last up to 13 months. The total study duration is anticipated to last a total of 15 months.

5.5 Pregnancy

Females may not participate in this study if they are pregnant, breastfeeding, were pregnant within the last three months or are planning a pregnancy during the course of the study. Date of last menstrual cycle will be recorded.

If the subject thinks they have become pregnant during the study it is important that they inform the study doctor immediately. If she becomes pregnant or thinks that she may be pregnant, she will be removed from the study and will ask to perform a final evaluation. The study doctor should refer her to seek obstetric care, the cost of which will be her responsibility. The study doctor may request to track the pregnancy and will report the pregnancy to the Sponsor and the IRB.

5.5 Right to Withdraw or Removal from Study

The subject is free to withdraw from this study at any time. The subject must inform the Investigator immediately if they intend to withdraw. To terminate the subject's participation in this study, they must contact the study doctor at the contact information listed on page one of the informed consent form. They will be asked to come to the study clinic or doctor's office to complete some end of study procedures which are listed in the Withdrawal Procedures section of the informed consent form. Their decision to participate in this study or to withdraw from this study will not influence the availability of their future medical care and will involve no penalty or loss of benefits to which they are otherwise entitled.

The Investigator in charge of the study can remove the subject from this study without their consent for any reason, including, but not limited to:

- a. His/her judgment that any condition or circumstance may jeopardize their welfare or the integrity of the study.
- b. Their failure to follow the instructions of the investigator(s).
- c. If the study is stopped by the sponsor and/or doctors participating in the study prior to completion.

5.6 Photography

Photos will be taken with an appropriate high resolution digital camera. It is important to record and carefully reproduce the camera settings (lighting, distance from the treatment area, background, polarization, etc.) at each visit, so that photos are suitable for comparison. If the subject does not wish to have their photos taken, they cannot be in the study.

5.7 Evaluation Methods

5.7.1 Tattoo Clearance

A photographic Scale will be used to evaluate outcomes. Blinded evaluators will grade the tattoo clearance of photographs taken of the subjects at baseline and post treatment. The results will be compared to determine improvement.

5.7.2 Investigator and Subject Questionnaires:

Questionnaires will be used to assess Investigator and Subject satisfaction at the 2 month follow up visit with their cosmetic results when compared to baseline photos using a six point scale ranging from “extremely satisfied” to “extremely dissatisfied”.

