5.7.3 Events

Recording of events will take place at all visits.

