7. ADVERSE REACTIONS

Side effects means anticipated reactions to treatment and typically resolve spontaneously. Anticipated events means reactions to treatment previously observed that may require medical intervention but are not serious in nature.

All adverse events that occur, starting from the time of the first treatment will be recorded in the Source Documents.

Adverse Events occurring will be captured and followed until the condition resolves, stabilizes, or is otherwise explained, or the subject is lost to follow-up. Subjects will be instructed that they may contact the Principal Investigator at any time throughout the course of the study.

The Investigator will review each event and assess its relationship to the laser treatments (not related, unlikely, possible, probable, and highly probable). The following definitions will be used for rating relationship to the laser treatments:

- Not related – The event is clearly related to other factors such as the subject’s clinical state, therapeutic interventions, or concomitant medications administered to the subject.
- Unlikely – The event was most likely produced by other factors such as the subject’s clinical state, therapeutic interventions, or a concomitant medication administered to the subject; and does not follow a known response pattern to the investigational product.
- Possible – The event follows a reasonable temporal sequence from the time of investigational product administration; and/or follows a known response pattern to the study sampling sessions; but could have been produced by other factors such as the subject’s clinical state, therapeutic interventions, or concomitant medications administered to the subject.
- Probable – The event follows a reasonable temporal sequence from the time of investigational product administration; and follows a known response pattern to the investigational product; and cannot be reasonably explained by other factors such as the subject’s clinical state, therapeutic interventions, or concomitant medications administered to the subject.
- Highly Probable – The event follows a reasonable temporal sequence from the time of investigational product administration; and follows a known response pattern to the investigational product; and cannot be reasonably explained by other factors such as the

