Adverse events, whether serious or non-serious, will be followed until the condition is resolved, stabilized, or otherwise explained, or the subject is lost to follow-up. Adverse events will be captured up to one week after a subject completes the study and where appropriate, medical tests and examinations will be performed to document the resolution of event(s). Outcomes may be classified as resolved, improved, unchanged, worse, fatal, or unknown (lost to follow-up). Following the resolution of any study-associated adverse events there will be no further adverse event reports for that subject.

PICOSURE/REVLITE

Risks to the subjects who participate in this study are the same as those for the subject undergoing infrared laser treatment. Eye injury due to direct ocular laser exposure requires the use of protective eyewear. with an optical density of 755nm- ≥ 7.0 OD, 532nm- ≥ 7 OD, 1064nm ≥ 7 OD.

Side effects of the laser treatment can include; Pain, blister, redness, swelling, bruising, pin point bleeding, crusting, itching, Some anticipated events from the treatment may include; infection, , allergic reaction, scarring, burn, hypopigmentation and hyperpigmentation.

Proper pre and post treatment standards and wound care reduces the risk of these

complications; however these conditions may or may not resolve over time.

Incomplete removal is relatively common,

Sunburn may occur if subject has unprotected exposure to ultraviolet (UV) light.

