15. DATA ANALYSIS

In order to meet the objectives of our clinical study we will analyze tattoo clearance scores, PI and Subject satisfaction, and events.

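### Masking is stated only for the clearance grade, so scarring, pigment change and satisfaction rest on ratings open to assessor bias; the evaluators already in place could also grade visible skin harm

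*Protocol*

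**What the plan says.** **Clearance.** Protocol section 5.7.1: "Blinded evaluators will grade the tattoo clearance of photographs taken of the subjects at baseline and post treatment". It does not say whether the evaluators are masked to laser, to time point or to both.

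**Satisfaction.** Section 5.7.2: "Questionnaires will be used to assess Investigator and Subject satisfaction at the 2 month follow up visit with their cosmetic results". The raters use a six-point scale against baseline photographs. No masking is mentioned.

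**Events.** Section 5.7.3: "Recording of events will take place at all visits". Section 7 adds: "The Investigator will review each event and assess its relationship to the laser treatments". The anticipated events listed there include "scarring, burn, hypopigmentation and hyperpigmentation".

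**Who sets the laser.** Section 5.3.3: "The appropriate parameters including the number of pulses will be determined by the physician".

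**Use of the data.** Section 15: "we will analyze tattoo clearance scores, PI and Subject satisfaction, and events", in order to meet the study objectives. Section 1 lists those as establishing treatment parameters, comparing with RevLite, and assessing safety.

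**Scope of the comparison.** Section 4 plans split-tattoo treatment for up to 10 of up to 100 subjects, and its wording allows one or both lasers.

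**The concern.** The protocol protects one outcome from knowledge of treatment and leaves the others unprotected. Whether a faint texture change counts as a scar, whether an event is possibly or probably related, and how satisfied a rater is with the result are all judgements that expectation can move. Section 3 gives that expectation a direction, since it says the shorter pulses may lead to better outcomes.

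Two uses of the data are exposed. One is any PicoSure-RevLite contrast of skin harm or satisfaction. The other is the choice of settings, where clearance has to be weighed against harm to the skin. The clearance grade as described measures ink removal only. It does not distinguish clean clearance from clearance accompanied by a scar or a pale patch, so that distinction depends on ratings with no stated masking.

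**Working it through.** This is mainly a question of who rates what, so the first step is to set the sections side by side.

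| Outcome analysed (section 15) | Rater | Masking stated in the protocol body |
|---|---|---|
| Tattoo clearance | Photograph evaluators (5.7.1) | Yes; masked to what is not said |
| Investigator satisfaction | Investigator (5.7.2) | None |
| Subject satisfaction | Subject (5.7.2) | None |
| Events, including scarring and pigment change | Investigator (7) | None |

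**Does the investigator know the laser?** The protocol never says so outright. It is an inference, but a strong one. The physician sets the parameters (5.3.3), and the two devices have different ranges (section 11): pulse width 0.5-0.8 ns against 5-20 ns, fluence 0.5-6 against 1.5-21 J/cm², and spot size 2-10 against 1.2-8 mm. They can hardly be set without knowing which device is in use.

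**Do split-tattoo subjects know?** The protocol body does not say. Protective eyewear is required (5.3.2), but nothing says that it hides the laser used.

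**Are outcomes recorded by part?** The protocol body describes neither the questionnaire nor the event record as separate for each part of a split tattoo. Without that, masking the subject would achieve nothing, because one score would cover both lasers.

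**Could visible harm be graded masked?** Yes, from existing material. Photographs are taken at baseline, at each treatment and at follow-up (5.4), and section 5.6 requires camera settings to be reproduced so that images can be compared.

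**The plan's own figures.** The SAP's 6 subjects per subgroup concerns the clearance grade, so it is not affected. The SAP gives neither a standard deviation nor a test, so the 6 cannot be confirmed. The enrolment figures do follow if 40% loss is assumed: 6 / (1 - 0.40) = 10 per group, and 10 × 10 = 100.

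**How much could rater bias matter?** The documents give no size, so this is illustration only. Assume that satisfaction is recorded by part, that the analysis is a paired t-test at two-sided 5%, that the lasers do not truly differ, and that knowledge of the laser shifts the within-subject difference by *b* standard deviations of that difference. The chance of a false finding is the probability that a noncentral t variable, with n - 1 degrees of freedom and noncentrality *b*√n, falls beyond the usual critical values. For *b* = 0.5 and n = 10 the noncentrality is 0.5 × √10 = 1.58.

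| Assumed bias *b* | n = 10 | n = 6 |
|---|---|---|
| 0 | 5% | 5% |
| 0.25 | about 11% | about 8% |
| 0.5 | about 29% | about 17% |
| 0.75 | about 56% | about 32% |

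Here 10 is the maximum number of split-tattoo subjects. The 6 is borrowed from the SAP's required number per subgroup, as a case with losses.

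**The case against.** The strongest reply is that the comparison at risk is barely planned. Safety is a non-comparative objective in section 1, met by recording side effects. No laser-against-laser contrast of harm or satisfaction is written down. Split treatment involves at most 10 subjects. This stands as a limit on scope: between-laser bias concerns those subjects only, and for the rest the issue is the weighing of harm against clearance across settings. It does not remove the point, because section 15 brings events and satisfaction to bear on all the objectives.

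Several stronger readings are tempting, and the documents do not support them:

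- *A reader might infer that skin damage goes unseen and such a setting simply counts as a success.* Events are assessed at every visit, graded for severity and relationship, and analysed. A scar or pale patch could also lower satisfaction. What is missing is a masked rating, not the capture of harm.
- *A reader might infer that the listed harms are permanent.* Section 7 classes them as anticipated events and leaves open whether they resolve. For that reason the documents do not support counting any such change at a 2-month (±1 month) visit as a treatment failure within a combined endpoint.
- *A reader might infer that subjects are told which laser was used.* The protocol body is silent. The consent form and case report form are appendices not available here, and they may address this or by-part recording.
- *A reader might infer that the clearance comparison, at least, is safely masked.* Section 5.7.1 does not say that the evaluators are masked to the laser.

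Photographs also cannot replace the investigator. Pain and itching cannot be seen in them, and texture change can be missed. That stands, and it is why the masked grade should be an addition only.

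**Conclusion.** The concern holds, within limits. Masking is stated for one outcome only. Visible skin harm is judged by an investigator who presumably knows the laser and settings, and satisfaction is rated by that investigator and by subjects whose masking is not addressed. Comparisons of these outcomes between lasers (up to 10 split-tattoo subjects), and the weighing of harm against clearance across settings, are open to assessor bias of unknown size. The percentages above show sensitivity to assumed biases and do not estimate what will happen.

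The conclusion rests on two inferences: that the physician who sets the parameters knows the device, and that the appendices add no masking. It is a worthwhile, low-cost improvement, and it does not invalidate the design.

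**What to change.** 1. **Section 5.7.1.** Have the same evaluators, stated to be masked to laser and settings, also grade visible scarring, hypopigmentation and hyperpigmentation on the photographs already taken. Do this separately for each part of a split tattoo, and define the grades in advance.
2. **Section 15.** Report these grades beside clearance. State that they supplement investigator event recording, which continues unchanged.
3. **Sections 5.7.2, 5.7.3 and the case report form.** In split-tattoo subjects, record events and satisfaction by tattoo part.
4. **Sections 5.7.2 and 15.** Report investigator ratings as open-label. Do the same for subject ratings unless subjects are kept unaware of which laser treated which part, and state which applies.

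The cost is slightly longer grading, a short grading scale with some evaluator training, and a protocol amendment with written IRB approval (section 19). No extra visits, photographs or subjects are needed. Two limits remain: photographs can miss texture change, and some subjects may guess the laser.

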5.7.3 Events

Recording of events will take place at all visits.

6. RISK MANAGEMENT

The investigator in this clinical trial has been invited to participate based on his previous experience with the use of laser systems in dermatology. Experience with laser treatments is the most critical element in managing subject risk in this trial. Additionally, all laser operators and subjects will wear protective eye glasses during the laser treatments. All other known risks will be disclosed to the subject via the informed consent process. Since this is an elective procedure and the subjects are volunteers, it can be assumed that their signature on the informed consent is indicative of their agreement to accept the risks involved.

7. ADVERSE REACTIONS

Side effects means anticipated reactions to treatment and typically resolve spontaneously. Anticipated events means reactions to treatment previously observed that may require medical intervention but are not serious in nature.

All adverse events that occur, starting from the time of the first treatment will be recorded in the Source Documents.

Adverse Events occurring will be captured and followed until the condition resolves, stabilizes, or is otherwise explained, or the subject is lost to follow-up. Subjects will be instructed that they may contact the Principal Investigator at any time throughout the course of the study.

The Investigator will review each event and assess its relationship to the laser treatments (not related, unlikely, possible, probable, and highly probable). The following definitions will be used for rating relationship to the laser treatments:

- Not related – The event is clearly related to other factors such as the subject’s clinical state, therapeutic interventions, or concomitant medications administered to the subject.
- Unlikely – The event was most likely produced by other factors such as the subject’s clinical state, therapeutic interventions, or a concomitant medication administered to the subject; and does not follow a known response pattern to the investigational product.
- Possible – The event follows a reasonable temporal sequence from the time of investigational product administration; and/or follows a known response pattern to the study sampling sessions; but could have been produced by other factors such as the subject’s clinical state, therapeutic interventions, or concomitant medications administered to the subject.
- Probable – The event follows a reasonable temporal sequence from the time of investigational product administration; and follows a known response pattern to the investigational product; and cannot be reasonably explained by other factors such as the subject’s clinical state, therapeutic interventions, or concomitant medications administered to the subject.
- Highly Probable – The event follows a reasonable temporal sequence from the time of investigational product administration; and follows a known response pattern to the investigational product; and cannot be reasonably explained by other factors such as the

subject's clinical state, therapeutic interventions, or concomitant medications administered to the subject; and either occurs immediately following investigational product administration, or improves on stopping the investigational product, or reappears on repeat exposure, or there is a positive reaction at the application site.

Each adverse event reported will be graded on a 3-point severity.

The following definitions for rating severity will be used:

- Mild – easily tolerated, causing minimal discomfort, and not interfering with normal everyday activities.
- Moderate – sufficiently discomforting to interfere with normal everyday activities.
- Severe – incapacitating and/or preventing normal everyday activities.

A Serious Adverse Event is any adverse device experience that results in any of the following outcomes: death, a life-threatening adverse device experience, in-patient hospitalization or prolongation of hospitalization, a persistent or significant disability/incapacity, or a congenital anomaly/birth defect. Important medical events that may or may not result in death, be life-threatening, or require hospitalization may be considered a serious adverse device experience when, based upon appropriate medical judgment, they may jeopardize the subject or subject may require medical or surgical intervention to prevent one of the outcomes listed in this definition

If any of the above adverse events are serious as defined by the FDA Code of Federal Regulations (CFR), Title 21, special procedures will be followed. All serious adverse events will be reported within 24 hours of acknowledgment to the Medical Monitor whether or not the serious events are deemed sampling session-related. All serious event reporting will adhere to 21 CFR part 812 and the IRB will be notified accordingly.

The Medical Monitor will enter the SAE information into the database and submit a desk copy of the complete SAE report to the files.

Adverse events, whether serious or non-serious, will be followed until the condition is resolved, stabilized, or otherwise explained, or the subject is lost to follow-up. Adverse events will be captured up to one week after a subject completes the study and where appropriate, medical tests and examinations will be performed to document the resolution of event(s). Outcomes may be classified as resolved, improved, unchanged, worse, fatal, or unknown (lost to follow-up). Following the resolution of any study-associated adverse events there will be no further adverse event reports for that subject.

PICOSURE/REVLITE

Risks to the subjects who participate in this study are the same as those for the subject undergoing infrared laser treatment. Eye injury due to direct ocular laser exposure requires the use of protective eyewear. with an optical density of 755nm- ≥ 7.0 OD, 532nm- ≥ 7 OD, 1064nm ≥ 7 OD.

Side effects of the laser treatment can include; Pain, blister, redness, swelling, bruising, pin point bleeding, crusting, itching, Some anticipated events from the treatment may include; infection, , allergic reaction, scarring, burn, hypopigmentation and hyperpigmentation.

Proper pre and post treatment standards and wound care reduces the risk of these

complications; however these conditions may or may not resolve over time.

Incomplete removal is relatively common,

Sunburn may occur if subject has unprotected exposure to ultraviolet (UV) light.

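### The only severity scale grades discomfort and interference with activities, so symptom-free scarring or pigment change is Mild by default whatever its visible extent

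*Protocol*

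**What the plan says.** Protocol section 7 sets one scale for all events: "Each adverse event reported will be graded on a 3-point severity". The lowest grade, Mild, is defined as "easily tolerated, causing minimal discomfort, and not interfering with normal everyday activities". To count as Moderate, an event has to be "sufficiently discomforting to interfere with normal everyday activities". The top grade, Severe, is kept for events described as "incapacitating and/or preventing normal everyday activities".

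The part of section 7 on the two lasers gives the anticipated events as "infection, , allergic reaction, scarring, burn, hypopigmentation and hyperpigmentation". It adds that good care lowers the risk, "however these conditions may or may not resolve over time". Section 7 also has a separate outcome code, which records whether an event cleared, improved, stayed the same or got worse.

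Efficacy is read from photographs (section 5.7.1): "Blinded evaluators will grade the tattoo clearance of photographs taken of the subjects at baseline and post treatment". Section 5.7.2 adds six-point satisfaction ratings by investigator and subject at the follow-up visit, made against the baseline photographs. Section 15 names clearance scores, satisfaction and events as the data to be analysed, and gives no further rule for events. The SAP is a sample size rationale and contains no safety grading.

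**The concern.** In tattoo removal, the harms that may outlast the treatment course are mostly changes in how the skin looks. The protocol names three of them. A severity scale built on discomfort and function suits pain, swelling or blistering, but has no criterion for how visible a mark is.

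All three objectives in section 1 are affected. Establishing treatment parameters and comparing PicoSure with RevLite both call for clearance to be set beside lasting skin change, and the third objective is safety itself. If the severity grade cannot tell a faint mark from a conspicuous one, a table of events by grade will not show a difference between lasers or settings in the extent of such marks. The up to 10 split-tattoo subjects (section 4) could give a within-person contrast on this point, but the grade as defined would not show a difference in extent between symptom-free marks.

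**Working it through.** No arithmetic is needed beyond a count and a visit window. The check applies the three definitions to the listed events and then asks whether another recorded item fills the gap.

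1. **What the grades measure.** Mild refers to tolerability, discomfort and activities. Moderate needs discomfort that interferes with activities. Severe needs incapacity or activities prevented. None mentions size, visibility, disfigurement or duration.

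2. **Applying them.** Take an area of hypopigmentation or a flat scar that causes no discomfort and limits nothing. It fails Moderate, because there is no discomfort that interferes with activities. It fails Severe, because nothing is prevented. Mild is the only grade left. The result is the same for a faint mark and for one that follows the whole outline of the tattoo.

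3. **How many listed events this touches.** The list has six: infection, allergic reaction, scarring, burn, hypopigmentation and hyperpigmentation. Three of the six (scarring and the two pigment changes) can be present without symptoms. A scar that hurts or restricts movement can be graded higher.

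4. **Other places where the information might be held.**
   - *Seriousness.* Section 7 describes anticipated events as non-serious, and its criteria for a serious event include disability and incapacity but no lasting cosmetic change.
   - *Outcome code.* A mark that stays can be coded as unchanged. That records its course. A small mark and a large one receive the same code.
   - *Satisfaction.* A scarred or depigmented site can be rated poorly. A low rating may equally come from ink that remains, and the rating does not say which.
   - *Clearance grade.* Section 5.7.1 names clearance as what is graded. The SAP describes the grading as 0 to 3, with a score of 2 tied to 50%. Neither mentions skin quality. The photographic scale itself is not reproduced.

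5. **What the visit timing can show.** Section 5.4 plans one follow-up at 2 months with a margin of 1 month, that is between 2 − 1 = 1 and 2 + 1 = 3 months. A finding there is persistence at follow-up. It does not establish permanence.

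**The case against.** The strongest reply is that this is an ordinary intensity scale being asked to do the work of several fields. The protocol also records the event by name, its relationship to treatment, its seriousness and its outcome. It follows events until they resolve or settle and takes photographs at baseline, treatment and follow-up visits. A lasting pigment change would therefore appear by name with an unchanged outcome, supported by photographs. Satisfaction with the cosmetic result is analysed as well. This largely stands: persistence is partly captured and cosmetic harm is not ignored. What remains missing is a grade of visible extent that is separate from residual ink.

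A second reply is that Mild is not forced. Its definition starts with easy tolerance, and a subject distressed by a mark may not meet it. An investigator might also count avoidance of social activity as interference. This stands in part. It means that the grade for a distressing but symptom-free mark is either Mild or undefined, and that investigators may differ. It does not open a route to Moderate for a mark that interferes with nothing.

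A third reply is that the Case Report Form (Appendix B) or the photographic scale may already hold a field for skin change. That cannot be excluded, and if so the point reduces to describing the field in the protocol.

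**Conclusion.** The point holds as a cheap improvement, not as an error or a contradiction. As written, symptom-free scarring, hypopigmentation or hyperpigmentation cannot be graded above Mild, and no other measure in the protocol or SAP text records its visible extent. The size is three of six listed anticipated events, limited to those without symptoms. How often they would occur in this trial is not given and is not estimated here. The conclusion assumes that the definitions are applied literally and that neither the Case Report Form nor the photographic scale supplies the missing item.

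Three stronger readings are tempting, and the documents do not support them:

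- A reader might infer that the plan puts harms in the wrong order, so that settings which damage skin would be preferred. Nothing in either document ranks harms by severity grade or selects parameters by it; section 5.3.3 leaves parameters to the physician.
- A reader might infer that pigment changes nearly always end up as Mild, or that the scale has only one working level for them. No figure in the documents supports a frequency, and symptomatic cases can be graded higher.
- A reader might infer that permanent harm is being hidden. The protocol says only that these conditions may not resolve, and the outcome code can show that they have not.

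**What to change.** Keep the three-point scale for symptomatic events. For scarring, hypopigmentation and hyperpigmentation, add a grade given by the blinded evaluators already planned, from the existing 2-month follow-up photographs compared with baseline. One possible form is none, just visible, clearly visible or marked, with:

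- written anchors for each level;
- adjacent untreated skin in frame, which section 5.6 does not now require;
- a not-gradable option where residual ink hides the skin.

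Report these grades, and the number of such events unresolved at last follow-up, beside the clearance score by laser and setting. Describe them as persistent at follow-up.

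The photographs and evaluators are already in the plan, so no visit, treatment or subject is added. The cost is some extra grading time, the work of writing anchors, and a safety table that may look less favourable. If the Case Report Form or photographic scale already has such an item, it is enough to describe it in sections 5.7 and 15.
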